2.1. Study Overview

This study is a randomized, placebo-controlled, double blind, parallel group, multicenter Phase III study, evaluating the safety and efficacy of voxelotor at 1500 mg and 900 mg dose level. Subjects meeting enrollment criteria were randomized in a 1:1:1 ratio to receive a daily dose of voxelotor 1500 mg, voxelotor 900 mg or placebo. The treatment duration was at minimum 12 weeks and may continue to a maximum of 72 weeks, with a key study endpoint of 24 weeks for the primary analysis of efficacy. The study will continue until all randomized subjects have reached Week 72 or discontinue from study early.

The study population includes SCD subjects with HbSS, HbSC, HbS β thalassemia, or other sickle cell syndrome variants. Subjects with 2 sickle hemoglobin genes (HbSS) or with compound heterozygosity for sickle Hb gene and beta thalassemia with no β globin expression (β 0 thal) thalassemia (HbS β 0 thal) are the SCD genotypes with most severe hemolysis and clinical symptoms. A history of at least one VOC in the past 12 months is required for enrollment. Subjects are also required to have Hb levels \leq 10.5 g/dL and \geq 5.5 g/dL.

SCD symptoms extend from infancy to adulthood. The population of this study includes adult and adolescent subjects (12 to 65 years).

Adolescent Subjects:

The study was to enroll only adult subjects initially. Adolescent subjects (ages 12 to <18 years) would be included in enrollment/randomization when:

1. Single dose PK data and modeling from Study GBT440-007 (pediatric subjects, 12-17 years of age) were available to confirm the appropriate dose for adolescent subjects, and
2. The DSMB had reviewed the safety data from at least 18 adults enrolled in this study of which at least 6 adults have received 1500 mg voxelotor for at least 4 weeks to confirm acceptable safety and tolerability before adolescents can be enrolled.

At the time that these criteria were met, adolescents would begin to enroll (as early as Group 1); a minimum of 50 adolescents would be included in the primary analysis of the study.

2.2. Study Measurements and Visit Schedule

Please refer to study protocol amendment 4 Appendix I for schedule of assessments.

3. OBJECTIVES

Primary Objective:

The primary objective is to assess the effect of voxelotor as measured by improvement in hemoglobin, compared to placebo.

Secondary Objectives:

The secondary objectives include the following:

- To assess the effects of voxelotor as compared to placebo on clinical measures of hemolysis, including unconjugated bilirubin, absolute reticulocyte, reticulocyte %, and LDH.
- To assess the effects of voxelotor as compared to placebo on long term Vaso-Occlusive Crisis (VOC).

Exploratory Objectives:

The exploratory objectives are to evaluate the effects of voxelotor compared to placebo on the following:

- Sickle Cell Disease Severity Measure (SCDSM),
- EuroQol EQ-5D-5L™ health questionnaire (EQ-5D-5L™),
- Clinical Global Impression Scale (CGI),
- Measures related to SCD pathophysiology and their utility as pharmacodynamic markers, e.g.,
 - Laboratory and clinical outcome measures including albumin creatinine ratio, scleral icterus, cholecystectomy and leg ulcers
 - Exploratory measures including RBC deformability and inflammatory markers
- School and/or work attendance and the use of opioid during the treatment period as recorded via eDiary,
- Time to first RBC transfusion and post baseline onset of VOC.
- Measures predictive of response to voxelotor.

Safety Objectives:

The safety objectives are to assess the safety of voxelotor based upon AEs, SAEs and SCD-related AEs, including VOC, acute chest syndrome (ACS) and Pneumonia, priapism, and osteonecrosis.

In addition, RBC transfusions, clinical laboratory tests, physical examinations, and other clinical measure events (e.g., discontinuations due to AEs, dose reductions) will also be evaluated.

Pharmacokinetic Objective:

The PK objective is to further assess the PK profile of voxelotor as evaluated by population PK analysis.

4. DEFINITIONS AND TERMINOLOGY

Study Drug

The term study drug refers to either voxelotor or placebo.

Baseline Value

Baseline measurements for efficacy and safety assessments will be the average of pre-treatment values (e.g., Screening and Day 1 pre-treatment). For PRO endpoints specific to SCD, e.g. TSS, the Baseline value is the average of the non-missing scores during the 28 to 35-day Screening period.

Day 1

Day 1 is the date of randomization.

Study Day

Study Day is defined relative to the date of randomization, i.e., Day 1.

For study assessments or events that occur on or after the date of randomization, the study day of an assessment/event is calculated as:

$$\text{Study Day} = \text{event date} - \text{Day 1 date} + 1.$$

For pre-randomization events, the study day is calculated as:

$$\text{Study Day} = \text{event date} - \text{Day 1 date}.$$

Study Visit

Study Visit is the nominal visit as recorded on the CRF.

Treatment Day

Treatment Day is defined relative to the date of initiation of study drug. This definition is essential when subjects are not dosed at Study Day 1, i.e. sometime after the date of randomization. Treatment day of an event that occurs on or after start date of dosing is calculated as:

$$\text{Treatment Day} = \text{Event date} - \text{Start Date of Dosing} + 1.$$

Extent of Exposure to Study Drug

Extent of exposure to study drug is defined as the number of weeks from initiation of study drug to the end of study drug treatment. Extent of exposure is calculated as follows:

$$\frac{(\text{End of Treatment Date} - \text{Start Date of Dosing} + 1)}{7},$$

Actual Exposure to Study Drug

Actual exposure to study drug is defined as the number of weeks from initiation of study drug to the last date of dosing of study drug which excludes days where treatment was entirely missed or intermittently stopped as recorded in the CRF. Duration of study drug exposure is calculated as follows:

$$\frac{\sum_{i=1}^n [\text{End Date of Dose}_i - \text{Start Date of Dose}_{i+1}] \times I_{\text{Dose}_i}}{7},$$

where n is the number of dose modifications during the study and

$$I_{\text{Dose}_i} = \begin{cases} 0, & \text{if treatment dose } i = 0 \text{ mg} \\ 1, & \text{if treatment dose } i \neq 0 \text{ mg} \end{cases}$$

Change from Baseline

Change from baseline for a given endpoint is defined as the Study Day value minus the Baseline value.

Hemoglobin Response at Week 24

Hemoglobin (Hb) response is based on the difference between the average value of Hb levels at Week 20 (Hb20) and Week 24 (Hb24) and baseline Hb level (HbB). A subject is considered to be a Hb responder if $[\text{mean}(\text{Hb20}, \text{Hb24}) - \text{HbB}] > 1 \text{ g/dL}$. If Hb20 or Hb24 is missing, then the calculation will use the non-missing Hb level. Regardless of calculated difference, subjects will be classified as a non-responder if any of the non-responder criteria in [Section 6.3.5.1](#) are met.

Hemoglobin Worsening at Week 24

- Severe anemic episode - worst Hb between weeks 12 and 24 inclusive is $< 5.5 \text{ g/dL}$
- Acute anemic episode - worst Hb between weeks 12 and 24 inclusive, is $\geq 5.5 \text{ g/dL}$ and $< 7 \text{ g/dL}$

Rate of Opioid Use During Treatment Period

The rate of opioid use is calculated as the number of days opioids were taken for SCD symptom management (as recorded in the eDiary) divided by the number of days with non-missing eDiary data from date of randomization to date of last dose.

Total Symptom Score (TSS)

For each subject, the TSS will be computed as follows: The Baseline TSS is the average of the scores during the 28 to 35-day Screening period. Similarly, post randomization when there is at least 75% compliance during a 4-week period, the TSS is the average score for each 4-week period. The 4-week periods are Weeks 1-4 (Study Day 1-28), Weeks 5-8 (Study Day 29-56), and Weeks 9-12 (Study Day 57-84) and follows similarly for subjects whose involvement exceeds 12 weeks up to Week 24. If there is a delay in initiating study treatment, all TSS data prior to administering treatment will be included with the Screening period data. All TSS data post dose through Study Day 28 will constitute Weeks 1-4. If missing data in a 4-week period is due to lack of compliance or subject dropout, the TSS will be set to missing for the 4-week period. Missing data due to VOC, VOC hospitalization or RBC transfusion will be imputed as described

in Section 6.3.5. Compliance of at least 60% during each 4-week period will also be examined in a sensitivity analysis for TSS.

TSS₁₀₀ is TSS rescaled from a 27-point scale to 100-point scale. Algebraically, this is accomplished as follows:

$$TSS_{100} = TSS \times \frac{100}{27}.$$

Clinical Global Impression of Change

The Clinical Global Impression of Change (CGIC) is a 7-point scale that requires study medical personnel to assess clinically meaningful change in a participant's sickle cell disease. The rating scale is as follows:

- Very much improved
- Moderately improved
- Minimally improved
- No change
- Minimally worse
- Moderately worse
- Very much worse

CGIC is assessed at Week 24, Week 48, End of Treatment (EOT), and End of Study (EOS).

Incidences of VOC, RBC Transfusion, ACS or Pneumonia On Study

Cumulative incidences of each named event is defined as the number of events from date of randomization to end of study, inclusive.

Time (in weeks) to First VOC

Time to first VOC during the study is defined as

$$(\text{Date of First VOC On Study} - \text{Date of Randomization} + 1) / 7.$$

Subjects who do not have a VOC will be censored at the end of study.

Time (in weeks) to First RBC Transfusions

Time to first RBC transfusions during the study is defined as

$$(\text{Date of First RBC transfusion On Study} - \text{Date of Randomization} + 1) / 7.$$

Subjects who do not have an RBC transfusion will be censored at the end of study.

Time (in weeks) to First ACS or Pneumonia

Time to first ACS or Pneumonia during the study is defined as

$$(\text{Date of First ACS or Pneumonia On Study} - \text{Date of Randomization} + 1) / 7.$$

Subjects who do not have an ACS or pneumonia will be censored at the end of study.

Adverse Event

An AE is defined as any untoward medical occurrence in a subject administered a pharmaceutical product during the course of a clinical investigation. For greater details, refer to Protocol Section 9.1.1.

All adverse events will be recorded on the Adverse Event CRF.

For this study's definition of a Serious Adverse Event (SAE), please refer to Protocol Section 9.1.2.

Treatment-emergent Adverse Event

A treatment-emergent adverse event (TEAE) is defined as an AE that emerges on or after initiation of study drug (having been absent pre-treatment), or an AE that existed pre-treatment and worsened on treatment (relative to the pre-treatment state) through 28 days after study drug discontinuation.

Treatment-emergent Laboratory Abnormalities

A Treatment-emergent Laboratory Abnormality is defined as any post-baseline laboratory assessment that emerges on or after initiation of study drug through 28 days after study drug discontinuation, which demonstrates an increase of 1 grade or more from the baseline toxicity value. If the baseline value is missing, any graded abnormality (grade 1 or higher) that occurs following initiation of study drug through 28 days after study drug discontinuation is deemed treatment-emergent.

Concomitant Medications

Concomitant medications are those medications taken on or after the initiation of study drug. This definition includes medications started prior to the initiation of study drug but continue concurrently with study drug.

Prior Medications

Prior medications are those medications taken prior to the initiation of study drug.

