5.2. Dose Modification

Participants should adhere to their assigned dose level. However, dose modification may be considered if warranted and as outlined below in [Sections 5.2.1](#) and [5.2.2](#).

All instances of study drug modification (dose reduction, interruption, or discontinuation) are to be captured in the participant research record and on the CRF. If the conditions/event leading to the dose modification have resolved, the original dose level should be resumed, unless in the judgment of the Investigator, this cannot be done safely.

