8.4.6. Safety and Tolerability Analyses

Safety analysis will be performed on all participants receiving at least one dose of study drug.

A treatment-emergent adverse event (TEAE) is defined as an AE that emerges on or after initiation of study drug (having been absent pretreatment), or an AE that existed pretreatment and worsened on treatment (relative to the pretreatment state). The incidence of TEAEs will be tabulated by system organ class (SOC), preferred term, severity and relationship to study drug.

AEs considered to be related by the Investigator will be summarized. Changes in laboratory parameters and vital signs over time will be summarized. Exposure-adjusted analyses may be performed to account for differences in exposure to study drug between treatment arms.

AEs will be reported by severity and relatedness to study treatment and classified according to Medical Dictionary for Regulatory Activities (MedDRA).

BPs, HR, and clinical laboratory data (hematology, serum biochemistry and coagulation) will be summarized.

For the laboratory safety data, out of range values will be flagged in the data listings and a list of clinically significant abnormal values will be presented.

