8.3.1. Summary of Exposure

Study drug administration will be summarized with number and percentage of subjects receiving from 1 to the maximum number of doses by treatment group. Similarly, the duration of treatment will be summarized with descriptive statistics.

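### The SAP's Actual Exposure formula sums over dose modifications rather than dosing records, so taken literally it gives 0 weeks to a participant whose dose was never modified

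*SAP*

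**What the plan says.** SAP Section 4 has two exposure measures. Extent of Exposure is the simple span from first dose to end of treatment, divided by 7.

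Actual Exposure is meant to remove time off drug. Its prose reads "Actual exposure to study drug is defined as the number of weeks from initiation of study drug to the last date of dosing", with the qualification "which excludes days where treatment was entirely missed or intermittently stopped as recorded in the CRF". The formula that follows sums a start-to-end difference for Dose i, multiplied by an indicator that is 0 when dose i is 0 mg and 1 otherwise, and divides by 7. The sum runs from i = 1 to n, "where n is the number of dose modifications during the study and".

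Protocol Section 5.2 says what a modification is: "All instances of study drug modification (dose reduction, interruption, or discontinuation) are to be captured". The same section expects participants to stay on their assigned dose.

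On use, SAP Section 8.3.1 says that "the duration of treatment will be summarized with descriptive statistics", without saying which exposure measure is meant. Protocol Section 8.4.6 adds: "Exposure-adjusted analyses may be performed to account for differences in exposure to study drug between treatment arms". SAP Section 8.2.3.3 plans an exposure-adjusted incidence of absence from school or work, again without naming the measure.

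**The concern.** The summand and its indicator are indexed by dosing record, but the upper limit counts modifications, which is a different quantity. An unmodified course has one record and no modifications. A hold followed by resumption has three records (on, off, on), but the protocol's list makes it one modification, since resumption is not listed.

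The formula therefore contradicts the prose above it for the dosing history that the protocol expects. Nothing else in the visible text redefines n or starts the index at 0.

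Actual Exposure is the only measure in SAP Section 4 that takes out holds and missed days. If it were programmed as written, person-time would disappear mainly from participants who took the drug without a change. The loss would depend on the number and timing of modifications, which can differ between arms.

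**Working it through.** The plan states no numerical result for actual exposure, so there is no figure to reproduce. The check applies the formula to simple dosing histories and compares it with the prose definition.

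Inputs:
- Upper limit n: the count of modifications (SAP Section 4).
- Modifications: reduction, interruption, discontinuation (Protocol Section 5.2).
- Indicator: 0 for a 0 mg record, otherwise 1 (SAP Section 4).
- Course lengths: 168 days (Week 24) and 504 days (Week 72), from SAP Table 1.
- Assumptions: the histories are hypothetical; records are contiguous; a hold is entered as a 0 mg record, as the indicator implies; completing treatment, or still being on drug at the cutoff, is not a modification.

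The summand is read in the way most favourable to the SAP:

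Actual exposure = [sum over i = 1 to n of (End_i - Start_i + 1) x I_i] / 7

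| Dosing history (treatment days) | n | Formula, weeks | Prose definition, weeks |
|---|---|---|---|
| 1-168, no change | 0 | empty sum = 0.0 | 168/7 = 24.0 |
| 1-504, no change | 0 | empty sum = 0.0 | 504/7 = 72.0 |
| 1-84, reduced dose 85-168 | 1 | 84/7 = 12.0 | 168/7 = 24.0 |
| 1-80, hold 81-85, 86-168 | 1 | 80/7 = 11.4 | (80 + 83)/7 = 163/7 = 23.3 |
| 1-56, hold 57-61, 62-112, hold 113-117, 118-168 | 2 | (56 + 0)/7 = 8.0 | (56 + 51 + 51)/7 = 158/7 = 22.6 |
| 1-84, then discontinued | 1 | 84/7 = 12.0 | 84/7 = 12.0 |
| 1-42, reduced dose 43-84, then discontinued | 2 | (42 + 42)/7 = 12.0 | 84/7 = 12.0 |

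The single-hold result is 1 - 80/163 = 51% too low. Counting the resumption as a second modification does not help: n = 2 adds only the hold record, and (80 + 5 x 0)/7 is still 11.4.

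The last two rows are right only because discontinuation is counted and supplies the missing unit. If it is not counted, they become 0.0 and 42/7 = 6.0. A discontinuer with an earlier hold and resumption has three records but two listed modifications, so the final record is lost even when discontinuation counts.

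With the sum taken over all records, every row equals its prose value.

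**The case against.** The strongest reply is that the intention is plain. The prose is clear, the summand is indexed by dose record, and a result of 0 weeks for a fully dosed participant is absurd enough that a careful programmer would correct it. SAP Section 8 requires verification by independent programming. The SAP's contents list includes a programming specifications section that we cannot see. Extent of Exposure is correctly defined and may be what the duration summary uses. All of this bears on the consequences and stands to that extent: we cannot say that any output was or would be wrong. It does not remove the contradiction between formula and prose, and independent programming works best when both programmers have one unambiguous definition.

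A reader might also infer more than the documents support:
- **That every participant is wrong.** Protocol Section 5.2 lists discontinuation as a modification, and on that count some early discontinuers come out right.
- **That the formula gives negative time.** In the text as read, the summand contains "Start Date of Dose}_{i+1". Subtracting the start of the next record would give -1 day for contiguous records. This is probably an artefact of reading the PDF: the neighbouring Treatment Day and Extent of Exposure formulas end in a plain + 1. Nothing above relies on it.
- **That all placebo participants get 0.** This needs mg to mean mg of voxelotor. SAP Section 4 defines study drug as either product, and Protocol Table 2 describes dose steps as one 300 mg capsule or tablet without distinguishing arms. It is an ambiguity to clear up, not a shown error.
- **That the pharmacokinetic analysis is affected.** SAP Section 2 places the population PK analysis in a separate document.

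**Conclusion.** The formula for Actual Exposure does not implement its own definition. Read literally, it returns 0 weeks for an unmodified participant (24.0 expected over 168 days). It also drops the final dosing record for a participant who completes treatment or is still on drug after a modification (11.4 instead of 23.3 weeks in the single-hold example). Early discontinuers may be correct, depending on whether discontinuation is counted and whether a resumption came before it.

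The point is small in reach. It concerns the descriptive duration summary in SAP Section 8.3.1, if that uses this measure, and any exposure-adjusted output built on it (Protocol Section 8.4.6, SAP Section 8.2.3.3). The primary endpoint and the fixed-sequence tests in SAP Section 6.3.3 do not use it. The sizes rest on illustrative histories, on holds being entered as 0 mg records, and on completion not counting as a modification. The 0-week result for an unmodified completer does not depend on how the summand's subscript is read.

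**What to change.** In SAP Section 4:
- Define n as the number of dosing records, a record being a contiguous period at one dose level, with holds entered as 0 mg records.
- Write the summand as (End Date of Dose i - Start Date of Dose i + 1) x I_i, with both dates from the same record, and divide the sum by 7.
- State that I_i = 1 when any study drug, voxelotor or placebo, was taken in record i, and 0 otherwise.

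Setting n to modifications plus 1 would not do. The single-hold example has one listed modification and three records, so the sum would stop at the second and again give 80/7 = 11.4 weeks. For a participant who simply discontinues, it would call for a record that does not exist.

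It would also help to name the exposure measure used in SAP Sections 8.3.1 and 8.2.3.3. The cost is a few lines of SAP text and a matching line in the programming specification. No new data are needed, and no clinical rule or hypothesis test changes.

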Statistical Methods	
STUDY ENDPOINTS
 
Primary Endpoint The primary efficacy measure is Hb response., defined as increase of Hb from baseline by > 1 g/dL at 24 weeks. Hb at 24 weeks is determined by the average value of Hb levels at Week 20 and Week 24.
 
Secondary Endpoints The secondary efficacy endpoints are as follows:
 
 • Change from baseline in hemoglobin at Week 24 • Change and percent change from baseline in hemolysis measures, including unconjugated bilirubin, absolute reticulocyte, reticulocytes %, and LDH at Week 24 • Incidence of severe anemic episodes (Hb < 5.5 g/dL) • Annualized incidence rate of VOC 
Exploratory Endpoints
 
 • Change from baseline in hemoglobin at Week 48 and Week 72

- Change from baseline in hemolysis measures: including unconjugated bilirubin, absolute reticulocytes, reticulocytes %, and LDH, at Week 48 and Week 72
- Time to first VOC. VOC is defined as:
 - A composite of acute painful crisis or ACS and includes the following:
 - Moderate to severe pain lasting at least 2 hours.
 - No explanation other than VOC.
 - Requires oral or parenteral opioids, ketorolac, or other analgesics prescribed or directed by a healthcare professional.
 - Must be documented in patient medical record that the patient was seen, or contacted the physician, within 1 business day of the event. The event may take place in a medical setting (hospital, clinic, emergency room).
- Time to first ACS or pneumonia
- Time to first RBC transfusion
- Rate of opioid use as recorded in the eDiary
- Sickle Cell Disease Severity Measure (SCDSM)
- EuroQol EQ-5D-5L™ health questionnaire (EQ-5D-5L™)
- Clinical Global Impression Scale (CGI)
- School and/or work attendance as recorded via eDiary

•
Safety Endpoint

- AEs, clinical laboratory tests, physical examinations, and vital signs

Pharmacokinetic Endpoint

- PK of voxelotor as evaluated by population PK analysis using nonlinear mixed effects modeling

SAMPLE SIZE

The sample size for the entire study, including Groups 1, 2 and 3, is estimated to be approximately 370 participants (up to a maximum of approximately 435 participants, depending on the dose[s] selected for the Group 3). Refer to the Study Schematic in [Figure 1](#).

For analysis purposes, data from all participants in Groups 1 and 2 will be combined to form the basis of the primary analysis of the study.

STRATIFICATION

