5. STUDY ENDPOINTS

Primary Endpoint:

The primary efficacy measure is Hb response at Week 24, as defined in [Section 4](#).

Secondary Endpoints:

The secondary efficacy endpoints are as follows:

- Change from baseline in hemoglobin at Week 24
- Change and percent change from baseline in hemolysis measures, including unconjugated bilirubin, absolute reticulocyte, reticulocytes %, and LDH
- Annualized incidence rate of VOC

Exploratory Endpoints:

- Change from baseline in hemoglobin at Week 48 and Week 72
- Change and percent change from baseline in hemolysis measures: including unconjugated bilirubin, absolute reticulocytes, reticulocytes %, and LDH, at Week 48 and Week 72
- Time to first VOC
- Time to first ACS or pneumonia
- Time to first RBC transfusion
- Rate of opioid use as recorded in the eDiary
- Sickle Cell Disease Severity Measure (SCDSM)
- EuroQol EQ-5D-5L™ health questionnaire (EQ-5D-5L™)
- Clinical Global Impression Scale (CGI)
- School and/or work attendance as recorded via eDiary

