6.3.4. Visit Windows

The blinded study period begins with the date of randomization, which is denoted in the protocol as Study Day 1. The conventions outlined below will be used to associate data measures, according to the study day corresponding to the date the data was collected, to an analysis visit window based on nominal (i.e., planned) visits, using the measure's study day relative to Day 1. Data collected before Study Day 1 will be considered screening information. Target study days, protocol acceptable ranges (per protocol) of study days for each scheduled assessment, and the analysis visit windows defined for each nominal visit day are shown in Tables 1 and 2.

If multiple assessments occur within a visit window, then the average of those assessments will be used for summarization and analysis.

Summarizations and analyses will utilize scheduled assessments and unscheduled assessments within a particular nominal window. Only central laboratory assessments will be included in summarizations and analyses of laboratory analytes.

Visit windows will be defined separately for non-PRO and PRO measures. PRO measures include ePRO Screening, ePRO SCD Severity Measure (SCDSM), eDiary data, EQ-5D-5L™, and CGI.

Table 1: Nominal Analysis Visit Windows for Non-PRO Measures

Nominal Visit Time	Target Study Day	Per Protocol Study Day Range	Study Day Range for Statistical Analysis*
Screening	-	[-35, -1]	[-35, -1]
Day 1	1	[-1, 1]	[-1, 1]
Week 2	14	[12, 16]	[2, 21]
Week 4	28	[26, 30]	[22, 35]
Week 6	42	[40, 44]	[36, 49]
Week 8	56	[54, 58]	[50, 70]
Week 12	84	[79, 89]	[71, 98]
Week 16	112	[107, 117]	[99, 126]
Week 20	140	[135, 145]	[127, 154]
Week 24	168	[163, 173]	[155, 210]
Week 36	252	[245, 259]	[211, 294]
Week 48	336	[329, 343]	[295, 378]
Week 60	420	[413, 427]	[379, 462]
Week 72	504	[497, 511]	[463, 545]

* Baseline is defined as the average of assessments on or prior the Study Day 1.

Table 2: Nominal Analysis Visit Windows for PRO Measures⁺

Nominal Visit Time	Study Day Range for Statistical Analysis[*]
Screening	[-35, -1]
Week 4	[1, 28]
Week 8	[29, 56]
Week 12	[57, 84]
Week 16	[85, 112]
Week 20	[113, 140]
Week 24	[141, 168]
Week 36	[169, 252]
Week 48	[253, 336]
Week 60	[337, 420]
Week 72	[421, 504]

* SCDSM scores on Study Days < -35 and Study Days > 168 will be excluded from SCDSM analyses

⁺ Notes:

(1) ePRO SCDSM is measured every day from the first day of Screening to Week 24 post randomization.

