8.2.1.2. Additional Analysis of Hb

Change from baseline in Hb over time up to Week 24 will be analyzed using a mixed effect for repeated measures (MMRM) model. The fixed effect terms include treatment, study visit, treatment by visit interaction, HU use at baseline, age group and geographic region. Baseline Hb will be a co-variate. Within-subject variability will be modeled using an unstructured covariance matrix. Missing data due to early drop out or missed visit will not be imputed for this analysis. Missing data due to VOC, VOC hospitalization or RBC transfusion will be imputed, as described in [Section 6.3.5](#).

Change from baseline in hemoglobin up to Week 48 and Week 72 will be analyzed similarly with available data as of the clinical cutoff date for the primary analysis.

The adjusted mean (lsmean) change from baseline in Hb at each visit, estimated from the MMRM model, with the estimated standard error and 95% confidence interval (CI), will be presented in tabular and graphic format. The difference in the adjusted means between treatment groups and the associated 95% CI of the difference will be provided.

Hb worsening will be summarized using a shift table for each treatment group. Incidences of post-baseline Hb < 5.5 g/dL will be summarized by treatment group, as well as incidences of Hb change from baseline < -2 g/dL.

Proportion of subjects with Hb of ≥ 10 g/dL at Week 24 will be explored.

All analyses specified above will be based on data with imputation for RBC transfusion, VOC and VOC hospitalization, as applicable. The analysis of Hb response rate will also be repeated using observed data without imputation to assess the robustness of the data.

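### Severe anemic episodes (Hb below 5.5 g/dL) are a protocol secondary endpoint missing from the SAP's secondary list, and the SAP's window-averaging rule, read as written, can lose such episodes but never add them

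*SAP*

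**What the plan says.** **Protocol.** The synopsis and Section 8.1.2 list "Incidence of severe anemic episodes (Hb < 5.5 g/dL" among the secondary endpoints, with no time frame. Section 8.4.1.1 plans a descriptive summary of post-baseline values below that threshold, on data imputed for transfusion and VOC.

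**SAP Section 5.** After "The secondary efficacy endpoints are as follows" come three items: Hb change at Week 24, the hemolysis measures and the annualized VOC rate. Severe anemic episodes are in neither this list nor the exploratory list, and the visible text gives no reason.

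**SAP Section 4 (Hemoglobin Worsening at Week 24).** "Severe anemic episode - worst Hb between weeks 12 and 24 inclusive" must be below 5.5 g/dL. A worst value from 5.5 to below 7 g/dL is an acute anemic episode.

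**SAP 8.2.1.2.** "Hb worsening will be summarized using a shift table for each treatment group", and "Incidences of post-baseline Hb < 5.5 g/dL will be summarized by treatment group". Then: "All analyses specified above will be based on data with imputation for RBC transfusion, VOC and VOC hospitalization, as applicable". The only observed-data repeat is for the responder endpoint: "The analysis of Hb response rate will also be repeated using observed data without imputation to assess the robustness of the data".

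**SAP 6.3.4.** "If multiple assessments occur within a visit window, then the average of those assessments will be used for summarization and analysis". Scheduled and unscheduled values both enter, and only central-laboratory values are used.

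**SAP 6.3.5.** Section 6.3.5.1 (Hb responder) replaces Hb after a transfusion not due to anemia with the last earlier value. After a transfusion due to anemia it assigns non-responder status and gives no replacement Hb. Section 6.3.5.2 replaces hemolysis results for 8 weeks from the transfusion date whatever the reason, for the MMRM and hemolysis-reduction analyses.

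**The concern.** A severe anemic episode is a threshold event: one value below 5.5 g/dL is the finding. The SAP's general data rules were written for visit means, change from baseline and responder status. Applied to a worst-value count, they can remove the value that the count is meant to find.

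A second value in the same window is a realistic event. Protocol 4.10 allows repeat testing to evaluate abnormal results, preferably at the central laboratory, so a low Hb may itself prompt the second sample that averages it away.

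What is at stake is whether a secondary endpoint is reported in a form that two programmers would derive identically. The unimputed laboratory summaries in SAP 8.3.4 do not fill the gap. With the statistics listed in SAP Section 8 they give the minimum per arm and visit, but not the number of patients below 5.5 g/dL.

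**Working it through.** **1. The SAP's own figures.** In the SAP 6.3.5.1 example the transfusion is on Day 114. The 8-week limit is 114 + 56 = Day 170, the 12-week limit is 114 + 84 = Day 198, and the Hb difference is 8.1 − 7.95 = 0.15 g/dL. All three reproduce. The documents give no rate or power for severe anemic episodes.

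**2. Averaging (SAP 6.3.4).** For two values x and y in one window, the window counts only if (x + y)/2 < 5.5, that is, if x + y < 11.0.
- 5.0 and 6.8: mean 5.9, lost.
- 5.0 and 6.0: mean 5.5, not below 5.5, lost.
- 5.3 and 5.6: mean 5.45, kept.

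These patient values are illustrative. For any number of values the mean is at least the minimum, so a mean below 5.5 implies a value below 5.5. Averaging therefore adds no severe episode. A patient drops out of the count only if no other window mean is below 5.5. If the Section 4 categories are derived the same way, a lost severe episode with a mean below 7 g/dL is relabelled as acute.

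**3. Room for a second value (SAP Table 1).** Each window contains one scheduled visit. Window lengths run from 14 days (Weeks 4 and 6) through 28 days (Weeks 12, 16 and 20) to 56 days (Week 24) and 84 days (Weeks 36, 48 and 60).

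**4. Size when a window has two values.** The documents give no within-patient variability, so this rests on assumption: two independent normal values, patient mean 6.0 to 7.0 g/dL, within-patient SD 0.4 to 0.8 g/dL. Among windows with at least one value below 5.5, the share lost by averaging runs from 59% (mean 6.0, SD 0.8) to nearly 100% (mean 7.0, SD 0.4, where such windows are very rare). A repeat taken soon after a low value would be correlated with it, which would lower the share. Windows with one value are unaffected.

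**5. Transfusion replacement, if applied to this count.** In the SAP example for a transfusion not due to anemia, 7.0 g/dL stands in for every Hb on Days 114 to 170 (170 − 114 + 1 = 57 days). That block contains the Week 20 and Week 24 target days (140 and 168). An observed 5.2 on Day 140 (illustrative) would be read as 7.0 and not counted.

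**6. The two time frames.** Table 1 window days through Week 24 are 69 (Weeks 2 to 8) + 140 (Weeks 12 to 24) = 209; Weeks 36 to 72 add 335, giving 544. The Weeks 12 to 24 definition covers 140/209 = 67% of the window days through Week 24 and 140/544 = 26% through Week 72. These shares matter only if that definition, and not the post-baseline count in SAP 8.2.1.2, is used for the endpoint.

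**The case against.** The strongest reply is that the SAP may already intend the right count. Worst Hb ordinarily means an individual minimum, and the qualifier *as applicable* in SAP 8.2.1.2 may mean that no imputation applies to a threshold count. The table and programming sections are redacted and could hold the selection rule. All of this is possible. None of it is stated in the visible text, whereas the averaging rule is stated and carries no exception. The SAP does refer to any post-baseline assessment when it defines treatment-emergent laboratory abnormalities; it has no matching wording about individual values for the 5.5 g/dL count.

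The reply is strongest on transfusion, and three stronger readings should be set aside.
- A reader might infer that every transfusion overwrites Hb for 8 weeks in this count, and that an earlier low value could be carried into Weeks 12 to 24 and create an episode. That extends SAP 6.3.5.2, which is limited to the MMRM and hemolysis-reduction analyses. The explicit Hb replacement, in 6.3.5.1, covers only transfusions not due to anemia and is written for the responder endpoint. Carry-in is a possible reading, not a stated rule.
- A reader might infer that the SAP dropped the endpoint. It did not: the incidence is still summarized in 8.2.1.2 in the same terms as protocol 8.4.1.1. What is missing is its place in the secondary list and a single definition.
- A reader might infer a bias toward voxelotor. Nothing in the documents gives a direction.

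The imputation clause is also not peculiar to the SAP; protocol 8.4.1.1 has essentially the same sentence.

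**Conclusion.** The point holds as a minor one. A protocol secondary endpoint is absent from the SAP's secondary list, two time frames stand side by side without a link to it, and the averaging rule read as written can only undercount severe episodes. Loss through transfusion replacement is conditional on applying 6.3.5.1 to this count, a question that 8.2.1.2 leaves open.

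The conclusion on averaging assumes that the general rule governs the count and that some windows hold two or more central-laboratory values. The documents give no frequency for this, so the number of affected patients cannot be derived. The endpoint is outside the fixed test sequence in both documents, so no alpha, power or confirmatory claim is affected.

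**What to change.** **In SAP 8.2.1.2**, define the incidence of Hb below 5.5 g/dL as the number of ITT subjects with at least one individual observed post-baseline central-laboratory value below 5.5 g/dL. State that it is exempt from the averaging in 6.3.4 and the imputation in 6.3.5. Report it through Week 24 and over all follow-up.

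**In SAP Section 5**, list this count as the protocol's severe anemic episode endpoint, secondary and descriptive.

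**In SAP Section 4**, say that the Weeks 12 to 24 categories serve the shift table, if that is the intent.

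**As sensitivity analyses**, show a count from scheduled visits only and the imputed version.

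**Cost.** A few sentences and one derivation from data already held. A count that includes unscheduled samples depends partly on how often each patient is sampled; the scheduled-only count makes that visible. Lows measured only at a local laboratory stay uncounted, as they are now.

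**Timing.** Data from 156 of 274 subjects (57%) have already been unblinded. Make the change before the remaining 118 in Group 2b are unblinded, which is when the SAP is to be final, or label the count post hoc.
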